NON-INTERVENTIONAL (NI) STUDY PROTOCOL

Study information

Title	Registry-based non-interventional analysis of advanced/metastatic renal carcinoma treatment patterns and outcomes in the Hospital district of Southwest Finland.
Protocol number	A4061098
Protocol version identifier	Version 1
Date	28 March 2022
Active substance	axitinib, ATC-code L01EK01 (previously L01XE17) sunitinib, ATC-code L01EX01 (previously L01XE04)
Medicinal product	Inlyta; Sutent
Research question and objectives	The aim of the study is to describe the characteristics, treatment pattern and outcomes of patients with advanced/metastatic renal cell carcinoma (RCC) with medical records in the HDSF data lake. The treatment sequence of mRCC patients and treatment outcomes (overall survival, time-to-next treatment) will be analysed with regard to individual risk score of the patient and over time. In addition, comorbidities, procedures and healthcare usage will be analyzed. As an exploratory objective, the coding practices especially with regard to risk score calculation are assessed.
Author	PPD [REDACTED], PhD, PPD [REDACTED] [REDACTED] email: PPD [REDACTED] tel. PPD [REDACTED]

PFIZER CONFIDENTIAL

[REDACTED]

TABLE OF CONTENTS

1. TABLE OF CONTENTS.....	2
2. LIST OF ABBREVIATIONS.....	4
3. RESPONSIBLE PARTIES	5
4. AMENDMENTS AND UPDATES.....	6
5. MILESTONES.....	7
6. RATIONALE AND BACKGROUND.....	7
7. RESEARCH QUESTION AND OBJECTIVES	9
7.1. Primary objectives	9
7.2. Secondary objectives.....	9
7.3. Exploratory objective	10
8. RESEARCH METHODS	11
8.1. Study design	11
8.2. Setting.....	11
8.2.1. Inclusion criteria	12
8.2.2. Exclusion criteria	13
8.2.3. Patient stratification	13
8.3. Variables.....	14
8.4. Data sources	16
8.5. Study size	17
8.6. Data management	17
8.7. Data analysis	18
8.7.1. Patient characteristics	18
8.7.2. Treatment patterns and treatment lines.....	19
8.7.3. Treatment outcomes.....	20
8.7.4. Morbidity	21
8.7.5. Healthcare resource utilization	21
8.7.6. Changes in coding practices over time	22
8.8. Quality control.....	22
8.9. Limitations of the research methods	22
8.10. Other aspects	23

9. PROTECTION OF HUMAN SUBJECTS	23
9.1. Patient information	23
9.2. Patient consent	23
9.3. Institutional review board (IRB)/Independent ethics committee (IEC)	23
9.4. Ethical conduct of the study	23
10. MANAGEMENT AND REPORTING OF ADVERSE EVENTS/ADVERSE REACTIONS	23
11. PLANS FOR DISSEMINATING AND COMMUNICATING STUDY RESULTS.....	24
12. REFERENCES	24
13. LIST OF TABLES	25

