6.3. Exploratory objective

1. Assess changes in coding practices over time, specifically IMDC risk score
 - a. including but not limited to changes in structured IMDC score recordings and the use of metastatic ICD-10 diagnosis codes (C77-C79)

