7.2.3. Patient stratification

Analyses will be stratified by:

- IMDC risk category (defined at the initiation of the first treatment for the metastatic RCC; see Table 1 and listing below for definitions)
 - Applied to all primary and secondary objectives
- Treatment line
 - Applied to primary objective 2 and 3

IMDC risk factors (each criterion accounts for +1 for the risk score):

1. Less than a year from time of initial RCC diagnosis to initiation of treatment for the metastatic RCC

2. Performance status* <80% (Karnofsky)
3. Hemoglobin* below normal (women < 117 g/l; men < 134 g/l)
4. Serum calcium* above normal (> 2.51 mmol/l)
5. Neutrophiles* above normal (> 6.3 x 10⁹/l)
6. Thrombocytes* above normal (> 350 x 10⁹/l)

** for performance status and laboratory values data of ± 3 months around the treatment initiation will be utilized due to possibly sparse data. If multiple records are available, the record closest to the treatment initiation will be utilized.*

Table 1. IMDC risk scores and categories based on two different approaches depending on the data coverage

	IMDC risk category	Total score of IMDC risk factors	Explanations/missing values
Option 1*	Favorable risk	0	no missing values allowed
	Intermediate risk	1-2	1) total score = 1; max 1 risk factor allowed to have missing value 2) total score = 2; no missing values allowed
	Poor risk	3 or more	max 3 risk factors allowed to have missing values
	Unknown risk**	-	when none of the above risk categories can be assigned
Option 2*	Appear favorable	0	all non-missing values for the risk factors indicate favorable risk max 3 risk factors allowed to have missing values
	At least intermediate	≥1	at least one risk factor criterion is met max 3 risk factors allowed to have missing values
	Poor	≥3	at least three risk factor criteria is met max 3 risk factors allowed to have missing values
	Unknown**	-	when none of the above risk categories can be assigned, i.e. more than 3 risk factors have missing value

** If small number of missing values is observed, the option 1 will be selected. If large number of missing values is observed and thus majority of patients were to belong to the “unknown” group of the option 1, the option 2 will be selected. The selection will be done after the data release and monitoring of data coverage.*

*** Patients with unknown risk category, will be analysed as own patient group.*

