7.7.3. Treatment outcomes

Primary objective 3:

The treatment outcomes will be assessed using time-to-event analysis, namely Kaplan-Meier fit or other relevant competing risk models. For each outcome, the time will be defined as follows (Figure 3):

- overall survival:
 - time from index until death (event) or end of study (censoring event)
 - when analysing by treatment lines, start the time from initiation of each treatment line
- progression free survival (PFS, defined using time to next treatment (TTNT) proxy):
 - time from initiation of the current treatment line until the initiation of the next treatment line (event), death (competing risk/event), or end of study (censoring event)

The Kaplan-Meier fits will be visualized, and the median survival/PFS of the patients will be reported as well, if reached.

Additionally, corresponding Cox proportional-hazards model will be fitted, including clinical variables as covariates (including but not limited to age, sex, IMDC risk score, diagnosis year, and treatment line number). The hazard ratios, 95% confidence intervals and p-values corresponding to each covariate will be reported.

[figure not shown]

Figure 3. Graphical illustration of definitions of treatment outcomes. Abbreviations: LOT = line of treatment.

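### IMDC Option 2 scores missing factors as zero, so a change in component recording over 2010-2021 would bias the IMDC-adjusted diagnosis-year hazard ratio

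*Combined protocol and SAP*

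**What the plan says.** Section 7.2.3 makes the IMDC category a stratifier for all primary and secondary objectives. Five of the six factors (performance status and four laboratory values) are taken from a window around treatment start "due to possibly sparse data". The sixth, time from diagnosis to treatment, comes from dates.

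Table 1 gives two scoring rules. Option 2 applies if most patients would be Unknown under Option 1. Its lowest category requires only that "all non-missing values for the risk factors indicate favorable risk". All three scored categories carry the same tolerance: "max 3 risk factors allowed to have missing values". The remaining patients are Unknown ("i.e. more than 3 risk factors have missing value") and form their own group. On the choice between the options: "The selection will be done after the data release and monitoring of data coverage".

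Section 7.7.3 lists the Cox covariates as "including but not limited to age, sex, IMDC risk score, diagnosis year, and treatment line number", and reports a hazard ratio, confidence interval and p-value for each. The study information table says that treatment sequence and outcomes "will be analysed with regard to individual risk score of the patient and over time". Section 6.3 sets the exploratory objective: "Assess changes in coding practices over time, specifically IMDC risk score". Section 7.7 rules out imputation. Nothing links a change in recording to the outcome models, and the limitations in section 7.9 do not mention it.

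**The concern.** Under Option 2 an unrecorded abnormal factor looks the same as a normal one. A patient can be placed too low but never too high. If fewer factors are missing in later years, patients who would earlier have been placed too low move up to their proper category. Each scored category then holds less sick patients late than early, with no change in anyone's disease or survival (a Will Rogers effect). A Cox model that conditions on this category assigns the difference to diagnosis year.

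The diagnosis-year hazard ratio is a reported result under primary objective 3. Section 5 describes rapid change in treatment over the period, so readers are likely to credit a falling hazard ratio to treatment. Any real treatment effect would be mixed with this artefact.

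**Working it through.** **The plan's own figure.** Section 7.5: 1,100 × 0.20 = 220 and 1,100 × 0.50 = 550, so the stated cohort size is reproduced. The treated mRCC cohort is smaller. The plan gives no event count, effect size or missingness rate.

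**Direction of misclassification.** Take time from diagnosis as known and normal, with m of the other five factors missing at random. A patient with s abnormal values among those five has observed score 0 with probability C(m,s)/C(5,s).

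| m missing | s = 1 | s = 2 | s = 3 |
|---|---|---|---|
| 0 | 0 | 0 | 0 |
| 1 | 1/5 = 0.20 | 0 | 0 |
| 2 | 2/5 = 0.40 | 1/10 = 0.10 | 0 |
| 3 | 3/5 = 0.60 | 3/10 = 0.30 | 1/10 = 0.10 |

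With m = 3 only two of the five are seen, so a patient whose true score of 3 lies wholly among them cannot be classed Poor. All errors are downward and grow with m.

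**Effect on the Cox model.** Survival was simulated with no trend by year and no change in true risk. Assumptions not in the documents:
- factor prevalences of 15-50%;
- hazard ratio of 1.3 or 1.6 per factor;
- about 70% events;
- time from diagnosis never missing;
- missingness of the other five changing linearly over 12 diagnosis years.

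Table 1 lets At least intermediate (1 or more) overlap with Poor (3 or more); these were taken as 1-2 and 3 or more. Section 7.7.3 does not say how IMDC is coded, so the category was used.

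For random missingness falling from 60% to 10%, with hazard ratio 1.6 per factor, 61% are Unknown under Option 1, so Option 2 is triggered. Mean true score in the first and last four years:

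| Option 2 category | First 4 years | Last 4 years |
|---|---|---|
| Appear favorable | 0.35 | 0.13 |
| Observed 1-2 | 2.06 | 1.68 |
| Poor | 4.11 | 3.82 |
| Unknown | 1.80 | 1.95 |

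The false diagnosis-year hazard ratio is 0.984 per year: 0.984^11 = 0.84 over 11 years, or 0.984^10 = 0.85 per decade.

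False hazard ratio over 11 years in the scenarios that trigger Option 2 (60,000 patients each, simulation error about ±0.03):

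| Missingness of the five factors | Unknown under Option 1 | HR 1.3 per factor | HR 1.6 per factor |
|---|---|---|---|
| Random, 60% to 10% | 61% | 0.89 | 0.84 |
| Random, 60% to 30% | 75% | 0.96 | 0.90 |
| Clustered by patient, 60% to 10% | 53% | 0.94 | 0.88 |
| Sicker patients missing more, 60% to 10% | 59% | 0.93 | 0.89 |
| Abnormal values recorded more often, 70% to 10% | 54% | 0.97 | 0.91 |
| Only normal values missing, 80% to 10% | 51% | 1.01 | 0.96 |

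As controls, the true categories or no IMDC term give 0.97-1.04 over all scenarios. Constant 50% missingness under Option 2 gives 0.96-1.00. A steeper trend, from a mean of 3 missing factors to 0, gives about 0.80 per decade with time from diagnosis known. This sets the lower end of the range.

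**At the study's size.** With 400 simulated studies per scenario, a false significant gain (hazard ratio below 1, two-sided p < 0.05, nominal 2.5%) occurred in about 3-10% at n = 220 and 4-15% at n = 550. The Monte Carlo standard error at 2.5% is √(0.025 × 0.975/400) = 0.008, so the lowest of these rates cannot be told from nominal.

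**Remedy.** Adding the number of missing factors brought the decade hazard ratio to between 0.96 and 1.04. In one run (60% to 10%, hazard ratio 1.6) it moved from about 0.87 to about 0.96, so the correction is not always complete. Dropping IMDC gave about 1.0.

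**The case against.** Several points against the concern are sound.

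- A reader might infer that recording improved. The documents do not say so. Section 6.3 asks an open question, and the items named there and in 7.7.6 are the structured score and the metastasis codes. Table 1 is built from dates, laboratory values and performance status, whose availability may have moved differently or not at all.
- A reader might infer that every category is affected. Unknown is kept separate and is not worse in early years.
- A bias as strong as 0.76 per decade can be produced, but only if all six factors are equally likely to be missing and the mean number missing falls from 3 to 0. Time from diagnosis should almost always be known.
- The bias shrinks when abnormal values are recorded more often. If they are half as likely to be missing as normal ones, the decade hazard ratio is about 0.92; at one quarter, about 0.98.
- If performance status alone drives the change, about a quarter of patients are Unknown under Option 1, and Option 2 is not selected.
- The labels Appear favorable and At least intermediate signal uncertainty. Sections 7.7, 7.7.6 and 7.8 provide for missingness reports and coverage checks, and whole-cohort results are reported too. Section 7.7.3 specifies no within-category comparison by calendar period.

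These points limit the size and certainty of the claim but do not remove it. Labels and missingness reports do not correct the adjusted hazard ratio. That Option 2 is conditional is weak comfort, because it is chosen when missingness is widespread. Keeping Option 1 is no full remedy either: in the same settings with improving recording it gives 0.87-1.00 over 11 years.

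**Conclusion.** The point stands in conditional form. It needs three things: Option 2 is selected, component recording changes with calendar year, and some missing values are abnormal. The scored categories then drift in meaning, and the IMDC-adjusted diagnosis-year hazard ratio is biased: below 1 with improving recording and, by the same mechanism though not simulated, above 1 with worsening recording.

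Under the assumed inputs, improving recording gives a false hazard ratio of roughly 0.80-0.97 per decade, and one near 1 if mainly normal values are missing. Prevalences, per-factor hazard ratios and missingness patterns are all assumptions.

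A reader might infer that the study will show a survival gain that did not occur. That is too strong: at 220-550 patients the false trend is usually not significant. The point estimate is still biased, and a larger cohort would not cure it. The safeguard should be written before data release, when the option is chosen.

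**What to change.** If Option 2 is selected:

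- **Section 7.7.3, main report.** Give the diagnosis-year hazard ratio both without and with the IMDC term.
- **Section 7.7.3, sensitivity model.** Wherever IMDC category and diagnosis year appear together, add the number of missing factors (0-3, categorical). Keep Unknown as its own level. It already means four or more missing, so the count needs no further level for it.
- **Section 7.7.6.** Report the number of missing components and the category shares by diagnosis-year period.
- **Interpretation.** State that an IMDC-adjusted time trend, or a within-category comparison over time, will not be read as a survival gain unless these analyses agree.

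The cost is protocol wording, up to three model degrees of freedom and one extra table, from data already held. The sensitivity model widens the confidence interval for diagnosis year. Its standard error rises by about 10-40%, most where missingness changes most with year (for example 0.027 to 0.038 per decade; 0.038/0.027 = 1.41).

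### Table 1, Option 2 files patients with four or five missing IMDC factors as Unknown even when a recorded factor already places them at intermediate risk or worse

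*Combined protocol and SAP*

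**What the plan says.** Section 7.2.3 (Patient stratification) scores six IMDC risk factors, where "each criterion accounts for +1 for the risk score". Table 1 gives two ways to turn the score into a category when values are missing. The choice is made after data release, and Option 2 is taken "If large number of missing values is observed and thus majority of patients were to belong to the “unknown” group of the option 1".

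Option 2 has four rows:

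- *Appear favorable* (score 0): "all non-missing values for the risk factors indicate favorable risk max 3 risk factors allowed to have missing values"
- *At least intermediate* (score 1 or more): "at least one risk factor criterion is met max 3 risk factors allowed to have missing values"
- *Poor* (score 3 or more): "at least three risk factor criteria is met max 3 risk factors allowed to have missing values"
- *Unknown* (all remaining patients): "when none of the above risk categories can be assigned, i.e. more than 3 risk factors have missing value"

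The footnote adds: "Patients with unknown risk category, will be analysed as own patient group". Section 7.7 (Data analysis) rules out imputation and exclusion for missing values. The IMDC category is the main stratifier (section 7.1), applies to all primary and secondary objectives (section 7.2.3), and is a covariate in the Cox model (section 7.7.3).

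**The concern.** *At least intermediate* is a lower bound. One recorded factor that is met establishes it, whatever the missing factors would have shown. A limit on missing values protects a label that missing data could overturn, and *Appear favorable* is such a label. *At least intermediate* is not. As written, Option 2 accepts an unproven *Appear favorable* with three factors missing, yet refuses an established *At least intermediate* with four missing.

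At stake is the content of two strata in the main stratification and the Cox covariate. The Unknown group would mix patients already shown to carry a risk factor with patients who have none recorded as met. The *At least intermediate* group would lose members that the recorded data place there. Because nothing is imputed, no later step restores the label.

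**Working it through.** **The plan's own figure.** Section 7.5 expects 20–50% of about 1,100 patients: 1,100 × 0.20 = 220 and 1,100 × 0.50 = 550. This reproduces. The point does not depend on it.

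**Inputs.** Six factors, each met, not met or missing; one point per met factor; the Option 2 rows as quoted. The documents give no missingness rates and no frequencies for the factors.

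**Step 1: all patterns.** There are 3^6 = 729. Unknown means four, five or six missing:

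| Missing | Unknown patterns | With at least one factor met |
|---|---|---|
| 4 | 15 × 2² = 60 | 15 × (2² − 1) = 45 |
| 5 | 6 × 2 = 12 | 6 × 1 = 6 |
| 6 | 1 | 0 |
| Total | 73 | 51 |

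**Step 2: factor 1 always known.** Factor 1 is "Less than a year from time of initial RCC diagnosis to initiation of treatment for the metastatic RCC". It carries no asterisk, so it lies outside the sparse-data note, and it needs only two dates. The patterns are then 2 × 3^5 = 486. Unknown now requires four or five of the other five factors to be missing:

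- four missing: 5 × 2 × 2 = 20 patterns, of which 5 × 3 = 15 have a met factor;
- five missing: 2 patterns, of which 1 has a met factor.

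That is 22 Unknown patterns, 16 of them with a met factor. One example is treatment within a year of diagnosis with no laboratory or performance-status record.

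**Step 3: what the limit does in each row.**

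- *Poor*: nothing. Three met factors leave at most three missing. With four or more missing, at most two can be recorded, so no Unknown patient has a score above 2.
- *Appear favorable*: it is needed, because missing factors could overturn the label.
- *At least intermediate*: it removes labels that the recorded data already establish.

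Option 1 has no such loss. In none of the 729 patterns does it return Unknown when the category is already determined.

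**Step 4: effect of the change.** Unknown falls from 73 to 73 − 51 = 22 patterns, or from 22 to 22 − 16 = 6 with factor 1 known. Every moved pattern goes to *At least intermediate*. No *Poor* or *Appear favorable* assignment changes.

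**Step 5: patients.** Pattern counts are not proportions of patients. The affected share is b × p, where b is the share with more than three factors missing and p the share of those with a met factor. Both are unknown. As an assumption, let each recorded factor be met independently with probability 0.1 to 0.5:

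- one factor recorded: p = 0.10 to 0.50;
- two recorded: p = 1 − 0.9² = 0.19 to 1 − 0.5² = 0.75.

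Then b = 0 gives 0. With b = 10%, b × p runs from 0.10 × 0.10 = 1% to 0.10 × 0.75 = 7.5%. With b = 30%, it runs from 3% to 22.5%.

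**The case against.** The strongest defence is that Option 2 applies one data-sufficiency rule to every category: at least three of six factors recorded. Without the limit, sparse-data patients are classified only if a factor is met. If factor 1 is always known, all 6 remaining Unknown patterns have factor 1 not met, so the group no longer means simply too little data. This stands as a real, small cost of the change. The protocol does not give this reason, and a lower bound remains true with any amount of missing data, so it does not justify the present rule. It does call for a sensitivity analysis.

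A second argument is that the label is only as sound as the recorded factor. The data lake is the only source (section 7.3), residence is required only at index (section 7.2.1), local disease before 2010 is admitted (section 7.2.2), and no start of look-back is stated. A first C64 record later than the true diagnosis could make factor 1 falsely met. This also stands, but it affects factor 1 wherever it is used.

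Third, a reader might infer that choosing Option 2 means that many patients have more than three factors missing. The documents do not support that. Option 1 returns Unknown for scores of 0 and 2 when a single factor is missing. One widely missing factor, such as performance status, could trigger Option 2 with nobody above three missing, and the effect would be zero. With factor 1 known, Unknown needs at least three of the four laboratory values absent from a window of three months either side of treatment start. Section 7.9 expects rather good data, and section 7.7 allows text-mining of the IMDC components.

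Fourth, a reader might infer that the information is lost to the study. It is not. The patients are kept as their own stratum, and section 7.7.1 summarises time from diagnosis to treatment, laboratory values and performance status separately. Only the category label is affected.

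**Conclusion.** The point holds on the plain text of Table 1, and no other section makes an exception. Under Option 2, any patient with four or five factors missing and at least one recorded factor met is filed as Unknown, although a score of 1 or more is already established.

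The logical part rests only on the scoring rule and on taking recorded values as correct. The number of patients cannot be derived from the documents. It is b × p, from about zero upward, and the percentages in the working rest on assumed inputs. A reader might infer that a sizeable fixed part of the cohort is misfiled, but nothing in the documents supports a figure. The effect arises only if Option 2 is chosen. The study is mainly descriptive and no *Poor* assignment is touched. The change is still worth making, because this category is the main stratifier and a Cox covariate and the correction is confined to one table.

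**What to change.** In Table 1, Option 2:

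- remove the limit on missing factors from the *At least intermediate* row;
- define Unknown as no recorded factor met and more than three factors missing;
- keep the limit for *Appear favorable*.

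Settle this before data release, since the choice between options is made afterwards. Report how many patients the change moves out of Unknown, and how many of those rest on factor 1 alone. Repeat the stratified and Cox results under the uniform limit as a sensitivity analysis. State in the report that the remaining Unknown group is selected for having no recorded factor met.

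The cost is a wording change in two rows of one table, one count and one repeated set of analyses. No new data are needed.
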